## 5.2 Protocol deviations

All IPDs (defined in Section 3.4) will be listed by treatment group and subject, and will include at a minimum, deviation type (as collected under the important deviation collection plan), deviation number, and deviation description.

A summary of number and percentage of subjects with an IPD will be produced by treatment group and overall for the RS. The summary will be overall (any IPD) and by type of deviation.

As described in Section 3.5, subjects may be excluded from the PPS based on major protocol deviations determined to have a potential effect on primary efficacy variables. Similarly, subjects with certain major protocol deviations may be excluded from the PK-PPS. Criteria for exclusion of subjects from the PPS or PK-PPS will be defined in a separate document developed in conjunction with a formal data review plan. To the extent feasible, rules for identifying major protocol deviations will be defined without review of the data and without consideration of the frequency of occurrence of such deviations. Important protocol deviations will be reviewed as part of the ongoing data cleaning process prior to database lock to identify those that are major and confirm exclusion from analysis sets. After all data have been verified/entered into a database and prior to database lock, a final data evaluation meeting will take place. The PPS will be confirmed at this time.

A by-subject listing of subjects excluded from each of the analysis datasets (for SS, FAS, PPS, and PK-PPS) will be prepared for the RS. The listing will include the categorized reason for exclusion as well as the specific reason.

## **6 DEMOGRAPHICS AND OTHER BASELINE CHARACTERISTICS**

By-subject listing will be produced for the ES for the demographics and for the RS for other baseline characteristics. All demographic and Baseline characteristics will be summarized descriptively for the FAS by treatment group and overall unless noted otherwise. The summary tables in Section 6 will be repeated by region.

### **6.1 Demographics**

Data collected on the Demographic CRF at the Screening Visit or at Baseline, include the date of birth, age (in years), sex (male, female), race (all categories on the CRF), ethnicity (Hispanic or Latino, not Hispanic or Latino), ethnic sub-group (Japanese, not Japanese), height (in cm), and weight (in kg). Demographics will be summarized for the RS, SS, and FAS.

Descriptive statistics presentation will adhere to the guidelines in Section 3.1. In addition, the following age categories will be summarized:

- $\leq 18$ , 19 -  $< 65$ , and  $\geq 65$  years
- 18 -  $< 65$ , 65 -  $< 85$ , and  $\geq 85$  years

Body mass index (BMI) and BMI categories ( $< 18.5$ , 18.5 to  $< 25$ , 25 to  $< 30$ , 30 to  $< 40$ ,  $\geq 40$ kg/m^2) will also be summarized.

Of note, the demographic table is required for data transparency reporting. The age categories are also required for the data transparency reporting.

### **6.2 Other Baseline characteristics**

- Randomization is stratified by region (Europe, North America, and Asia), and by current use of AEDs with binding to SV2A proteins, such as LEV and/or BRV (yes or no). The percentages of subjects in each stratum for each stratification factor will be summarized for the RS.
- Lifestyle information (alcohol and illicit drug use) obtained at the Screening Visit (Lifestyle CRF) will be listed for the RS. These variables will be summarized descriptively (number and percent of subjects in each category) for the SS.

### **6.3 Medical history and concomitant diseases**

#### **6.3.1 Medical history and ongoing medical conditions**

Medical history and ongoing medical conditions will be listed and summarized for the SS by MedDRA system organ class (SOC) and preferred term (PT). The start date (month and year only) and end date (or ongoing if applicable) will be included in the listing. Epilepsy history will not be included in these tables. Procedure history will be listed separately by the procedure reported term.

### **6.3.2 Procedure history**

Procedures or surgeries prior to study entry will not be summarized and will only be provided in subject data listing.

### **6.3.3 Medical history of epilepsy**

The history of epilepsy data will be listed for all subjects in the RS. The following summaries will be produced by treatment group and overall using the FAS unless otherwise specified:

#### **6.3.3.1 Etiology of epilepsy**

The number and percentage of subjects with each type of etiology as specified in the Etiology of Epilepsy CRF will be presented.

#### **6.3.3.2 Epilepsy surgery status**

Epilepsy surgery status parameters are collected on the Epilepsy Surgery Status CRF. The number and percentage of subjects who are evaluated for epilepsy surgery and in each of the outcome category will be presented.

#### **6.3.3.3 Epileptic seizure profile**

Epileptic seizure profile is based on the historical seizure types reported by the subject on the ILAE Seizure Classification History form. The number and percentage of subjects experiencing each seizure type at any time in the past will be summarized.

#### **6.3.3.4 Focus localization**

The number and percentage of subjects with each category of focus localization (unknown, frontal, temporal, parietal, occipital) will be summarized. Subjects may be counted in more than one category of focal localization.

#### **6.3.3.5 History of epileptic seizures and diagnosis of epilepsy**

History of epileptic seizures are collected on the History of Epileptic Seizures CRF. The summary will present the number and percentage of subjects with a history of status epilepticus, the number and percentage of subjects with a history of withdrawal seizures, and quantitative summaries of time since the first seizure relative to the date of Visit 1, time since last seizure relative to the date of Visit 1, and age at onset of first seizure.

The date of diagnosis of epilepsy is collected on Diagnosis of Epilepsy CRF. The duration of epilepsy will be derived from the date of first diagnosis relative to the date of Visit 1. The duration of epilepsy and age at epilepsy diagnosis will be summarized descriptively.

#### **6.3.3.6 Historical seizure count and cluster count**

The Historical Seizure Count and Historical Cluster Count CRF records the number of seizures and clusters experienced by the subject during the past 2 months prior to the Screening Visit. The number of seizures and clusters will be summarized by seizure type and month.

#### **6.3.3.7 Seizure types experienced during the Baseline Period**

The number and percentage of subjects experiencing each seizure type during the Baseline Period will be summarized based on data from Seizure Count CRF.

### **6.3.3.8 Baseline focal seizure frequency**

The 28-day adjusted frequency of observable focal-onset seizures (Types IA1, IB, and IC) and of all Type I focal-onset seizures during the Baseline Period will be summarized. Seizure counts are collected by diary; calculation of the Baseline 28-day adjusted frequency is provided in Section 3.3.1.

### **6.3.3.9 Brain magnetic resonance imaging (MRI)**

MRI data will be provided in the subject listing.

## **6.4 Prior and concomitant medications**

In this study, AED medications are collected separately from prior and concomitant non-AED medications. Handling of AED and non-AED medication is described in the following sections. AED medications will be summarized for the FAS, non-AED medications will be summarized for the SS.

### **6.4.1 AED medications**

Each concomitant medication will be classified as either an AED or a non-AED medication. AED medication taken and stopped prior to the Visit 1 will be reported on the History of Previous Antiepileptic Drug Treatment CRF. AED medication that started prior to Visit 1 and which is ongoing or AED medication prescribed during the study will be recorded on the AED Medication CRF.

- Previous AEDs are AEDs taken and stopped prior to the Visit 1. Previous AEDs are reported on History of Previous Antiepileptic Drug Treatment CRF.
- AEDs taken at study entry are reported on AED CRF and if:
  - (start date of medication) < (the date of Visit 1) and (stop date of medication) ≥ (the date of Visit 1) or ongoing
- Prior AEDs include both previous AEDs and AEDs taken at study entry
- Concomitant AEDs are reported on AED CRF and if:
  - (start date of medication) ≤ (stop date of IMP) and (stop date of medication) ≥ (start date of IMP) or ongoing
  - start date of medication is unknown but (stop date of medication) ≥ (start date of study drug) or ongoing.

The number and percentage of subjects taking AED medications will be summarized by chemical/therapeutic/pharmacological subgroup (ATC classification level 4), and preferred drug name. The following summaries of AED medications will be produced for the FAS by treatment group and overall:

- Previous AEDs from the History of Previous Antiepileptic Drug Treatment CRF
- Number of previous AEDs taken: <4, 4-5, 6-7, 8-10, >10 AEDs.

- Previous AEDs by reason for AED discontinuation: The number and percentage of subjects by reason for discontinuation of previous AEDs will be summarized. Percentages for each reason for discontinuation will be relative to the number of subjects taking each AED.
- AEDs taken at study entry
- Number of AEDs taken at study entry: 1, 2, 3, and >3AEDs
- Prior AEDs
- Number of prior AEDs: <4, 4-5, 6-7, 8-10,>10 AEDs.
- Concomitant AEDs

#### **6.4.2 Use of vagus nerve stimulation**

Vagus Nerve Stimulation (VNS) status at Screening (VNS Status at Screening CRF) will be summarized as the number and percent of subjects with VNS at screening and as number and percent of subjects with VNS turned on. Subjects with VNS at screening and setting changed during treatment period will also be summarized. All other VNS data will be provided in subject data listings and will not be summarized for the FAS.

#### **6.4.3 Prior and Concomitant non-AED medications**

Medications recorded on the Prior and Concomitant Medication CRF should not include AEDs. Non-AED medications will be analyzed separately from AED medications.

- A prior non-AED medication if:
  - (start date of medication) < (start date of IMP)
  - start date of medication is unknown but (stop date of medication) < (start date of IMP)
- A concomitant non-AED medication if:
  - (start date of medication)  $\leq$  (stop date of IMP) and (stop date of medication)  $\geq$  (start date of IMP) or ongoing
  - start date of medication is unknown but (stop date of medication)  $\geq$  (start date of study drug) or ongoing.

The number and percentage of subjects taking non-AED medications will be summarized by anatomical main group (Anatomical Therapeutic Chemical [ATC] classification level 1), therapeutic subgroup (ATC classification level 2), and preferred drug name. The following summaries of non-AED medications will be produced for the SS by treatment group and overall:

- Prior non-AED
- Concomitant non-AED

## **7 MEASUREMENTS OF COMPLIANCE**

### **7.1 Treatment compliance**

The IMP will be provided in blister-packed treatment cards, each providing 3, 4, or 7 days' treatment of active or placebo (plus some reserve tablets in case of unexpected event). At each

visit after IMP is dispensed and at the end of the Taper/Conversion Period, subjects must return all unused IMP and empty IMP containers. IMP is dispensed at Visits 2, 3, 4, 5, 6, and 7. IMP return and IMP accountability evaluation occurs at Visits 3, 4, 5, 6, 7 and 8. Drug accountability is recorded on the Drug Accountability form.

Measurement of treatment compliance with the dosage schedule will be based on dispensed and returned pill counts. Drug accountability data will be listed (SS) by treatment group and study visit. The listing will include dispense date and number of pills dispensed; return date and number of pills returned.

Subjects are instructed to take medication bid, approximately 12 hours apart. Based on the PSL tablet mg amounts provided, subjects will take 10 tablets per day (some containing PSL, some placebo) during the Titration and Taper (subjects not entering the EP0093 OLE) periods. They will take 12 tablets per day (some containing PSL, some placebo) during the Stabilization, Maintenance, and Conversion (subjects entering the EP0093 OLE) periods. Compliance during the entire 16-week Treatment Period, Titration and Stabilization Period, and the Maintenance Period will be calculated as 100 times the actual number of tablets taken over the evaluation period (based on the Study Medication Administration CRF), and dividing this quantity by the number of tablets that should have been taken during this period of time.

The number of tablets expected (that should be taken) during the periods of interest are:

- 16-week Treatment Period:  $10 \times \text{duration of Titration Period (days)} + 12 \times \text{duration of Stabilization Period and Maintenance Period (days)}$
- Maintenance Period:  $12 \times \text{duration of the Maintenance Period (days)}$
- Titration and Stabilization Period:  $10 \times \text{duration of Titration Period (days)} + 12 \times \text{duration of Stabilization Period (days)}$

Duration of an analysis period in days will be calculated as date of the last dose of IMP in a period - date of the first dose at the specific period +1. Compliance is only computed for actual time of participation in the study up to the last dose of IMP during the Treatment Period. If a subject didn't enter an analysis period, the compliance for the analysis period will not be calculated.

Percent compliance will be summarized for the FAS using descriptive statistics for each treatment group and overall. In addition, the number and percentage of subjects with compliance <75%, 75% to 125%, and >125% will be summarized.

## 7.2 Diary compliance

Primary and secondary, and other efficacy variables are based on diary-collected seizure frequencies, and as such, diary compliance will be evaluated along with treatment compliance. Subjects are instructed to complete their diary entries at least once a day during the study. A diary day will be considered missing for compliance if the seizure count field is checked as 'not done'. Diary compliance will be evaluated during the Baseline Period, during the entire 16-week Treatment Period, and during the Maintenance Period.

Diary compliance will be calculated as 100 times the number diary days (days with diary completed) during the period and dividing this quantity by the expected number of diary days that should have been completed during this period of time. Compliance is only computed for

actual time of participation in the study up to the end of the Treatment Period. Only data prior to and on the date of last dose of study medication will be included in the compliance calculation. If a subject didn't enter an analysis period, the diary compliance for the analysis period will not be calculated.

Diary compliance data will be listed by subject. Percent diary compliance will be summarized for the FAS, by period using descriptive statistics for each treatment group and overall. In addition, the number and percentage of subjects with compliance  $\leq 80\%$  and  $> 80\%$  will be summarized.

## 8 EFFICACY ANALYSES

Unless noted otherwise, analyses of efficacy endpoints will be performed on the FAS. Additional analyses of selected efficacy endpoints will be performed using the PPS as described in the sections below. For the efficacy variables described below, seizure frequency refers to a 28-day adjusted frequency; observable focal-onset seizures refer to Type IA1, IB, and IC (ILAE Classification of Epileptic Seizures, 1981); focal-onset seizures include all Type I seizures; and seizure-free status and seizure-free days include all seizure types (Types I, II, and III). Only seizure data prior to and on the date of last dose of study medication will be included in the analysis. Unless noted otherwise, all efficacy tables will be presented by treatment group.

As listed in Section 2.3.1, separate primary and secondary seizure frequency efficacy variables have been designated for submission to FDA and submission to European regulatory agencies along with other seizure frequency efficacy variables used for both submissions. A summary of seizure frequency variables and status as primary or secondary is presented in Table 8-1.

**Table 8–1: Summary of seizure frequency variables**

Variable	12-Week Maintenance Period			16-Week Treatment Period		
	Observable Focal Onset (IA1, IB and IC)	Focal Onset (All Type I)	All Seizures (Type I, II and III)	Observable Focal Onset (IA1, IB and IC)	Focal Onset (All Type I)	All Seizures (Type I, II and III)
Change in log-SF	X (a)(c)	X		X		
75% RR	X (b)(c)	X		X		
50% RR	X (c)	X		X		
Percent Reduction in SF	X (c)	X		X	X	
90% RR	X	X				
100% RR	X	X				
Change in log-SF (4-week intervals)	X					
Seizure Freedom			X			X
Number of seizure-free days			X			X
Cumulative RR				X	X	

**Table 8–1: Summary of seizure frequency variables**

Variable	12-Week Maintenance Period			16-Week Treatment Period		
	Observable Focal Onset (IA1, IB and IC)	Focal Onset (All Type I)	All Seizures (Type I, II and III)	Observable Focal Onset (IA1, IB and IC)	Focal Onset (All Type I)	All Seizures (Type I, II and III)
Change from baseline in seizure frequency	X	X		X	X	

RR=Responder Rate. SF=Seizure Frequency.

(a) Primary endpoint for FDA, PMDA and other Regulatory agencies not referencing EMA

(b) Primary endpoint EMA

(c) Secondary Endpoint

## 8.1 Statistical analysis of the primary efficacy variables

### 8.1.1 Derivations of primary efficacy variables

#### 8.1.1.1 Seizure frequency

Seizure frequency (SF) refers to the 28-day adjusted seizure frequency. The 28-day adjusted seizure frequency is defined as:  $SF = (\text{Number of Seizures}) \times (28 / D)$ . The number of seizures is the total number of seizures during an analysis period or time interval. For cluster seizures, the number of cluster episodes will be included. D corresponds to the number of days for which the diary was available during the analysis period or time interval.

#### 8.1.1.2 Change in log-transformed seizure frequency from Baseline

The 28-day adjusted seizure frequency value will be log-transformed using the function  $\ln(x+1)$ , where  $\ln$  represents the natural logarithm function. The change in the log-transformed seizure frequency from Baseline is calculated as:  $\ln(SFT+1) - \ln(SFB+1)$ , where SFT corresponds to the seizure frequency during an analysis period and SFB corresponds to the Baseline period seizure frequency.

For the primary efficacy variable for the FDA, SFT and SFB are the observable focal-onset seizure frequency during the 12-week Maintenance Period and Baseline Period, respectively.

#### 8.1.1.3 Percent reduction in seizure frequency from Baseline

The percent reduction in seizure frequency (PRD) from the Baseline is defined as:  $PRD = [(SFB - SFT) / SFB] \times 100$ , where SFT corresponds to the 28-day adjusted seizure frequency during an analysis period and SFB corresponds to the Baseline seizure frequency. A negative PRD indicates an increase in seizure frequency from Baseline.

#### 8.1.1.4 75% Responder

Responder status (yes or no) for a subject is determined by the percent reduction in seizure frequency (PRD) from Baseline. A subject is defined as a 75% responder if s/he has a reduction in seizure frequency (PRD) of at least 75% from the Baseline. The 75% responder rate (RR) will be calculated as the proportion of 75% responders. For the primary efficacy variable for the

EMA, 75% responder status is calculated based on the percent reduction (PRD) from the Baseline in observable focal-onset seizure frequency during the 12-week Maintenance Period.

## **8.1.2 Analysis of the primary efficacy variables**

### **8.1.2.1 Primary variable for submission to the US FDA, PMDA, and other regulatory authorities not referencing EMA**

The primary efficacy variable for the US FDA/PMDA is the change in log-transformed observable focal onset seizure frequency from Baseline, over the 12-week Maintenance Period. Analyses of the primary variable for the FDA will be performed on the FAS as described below.

Change from Baseline in observable focal-onset seizure frequency (using the log-transformed data) will be analyzed for the FAS using analysis of covariance (ANCOVA) with treatment group (PSL 400mg bid, 200mg bid, 100mg bid, 50mg bid, and placebo) as the main factor, Baseline log-transformed seizure frequency as a continuous covariate, Baseline SV2A use (Yes or No), and Region (Europe or Non-Europe) as factors. Pairwise contrasts will be constructed to compute estimated effects of each dose from placebo.

Treatment effects will be characterized using treatment differences based on back-transformation of least squares (LS) means obtained from the above ANCOVA model. Percent reduction over placebo will be calculated as  $100 \times (1 - \exp(\text{diff}))$ , where diff is the model estimate of the log ratio between each PSL group and placebo group. Similarly, estimates for the upper and lower bounds of the 95% confidence interval (CI) will be back-transformed for table presentation as  $\exp(\text{lower})$  and  $\exp(\text{upper})$ , respectively, where upper and lower correspond to the 95% CI of the log ratio. If there are issues with convergence, covariates will be dropped sequentially in the order of Region, and then Baseline SV2A use (Yes or No) if further needed.

Pairwise comparisons of the 400mg bid, 200mg bid, and 100mg bid PSL dose groups versus placebo will be carried out using the analysis model described above. Type 1 error will be controlled using the Hochberg step-up procedure (Section 4.5) within SAS® Proc Multtest. If all the results of the 3 pairwise comparisons are statistically significant, then the 50mg bid dose group will be compared to placebo, too. Both multiplicity-adjusted and unadjusted p-values will be presented.

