13.3.1 Analysis of the primary efficacy variable

13.3.1.1 Analysis of the primary efficacy variable for the US FDA, PMDA, and other regulatory authorities not specified in Section 4.1.1.2

Pairwise comparisons of 400mg, 200mg and 100mg dose groups versus placebo will be carried out using the analysis model below. Type 1 error will be controlled by the Hochberg step-up procedure within SAS® Proc Multtest. If all the results of the pairwise comparisons are statistically significant then the 50mg dose group will be compared to placebo.

For the US FDA, PMDA, and other regulatory authorities not specified in Section 4.1.1.2, the primary efficacy variable is the change in log-transformed observable focal-onset seizure frequency from Baseline, over the 12-week Maintenance Period. The 28-day Baseline and post-Baseline (maintenance) seizure frequency will be transformed with the natural logarithm, specifically $\ln(x+1)$, where x represents the 28-day seizure frequency. The transformed seizure frequency data will be analyzed using analysis of covariance (ANCOVA) with treatment group

as the main factor, Baseline log-adjusted seizure frequency as a continuous covariate, and Baseline SV2A use and Region as categorical factors. Pairwise contrasts will be constructed to compute estimated effects of each dose from placebo.

All pairwise analyses of the primary efficacy variable will be repeated on the PPS.

13.3.1.2 Analysis of the primary efficacy variable for EMA and regulatory authorities who reference EMA

For EMA and regulatory authorities who reference EMA, the primary efficacy variable will be the 75% responder rate in observable focal-onset seizures during the Maintenance Period and will be analyzed using logistic regression with factors for treatment group, Baseline seizure frequency, Region, and Baseline SV2A use. If there are issues with convergence, Baseline SV2A use will be dropped.

The same methodology carried out in Section 13.3.1.1 will be applied to the pairwise analyses.

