**Figure 2–1: Study design**

## 2.7 Determination of sample size

The sample size was calculated based on achieving 90% power to observe a statistically significant result for either the 400mg bid and 200mg bid or 200mg bid and 100mg bid doses when compared to placebo, for a change from Baseline of the log-transformed ( $\ln x + 1$ ) 28-day adjusted seizure frequency. Multiplicity is controlled for using the Hochberg step up procedure.

The log-reduction from Baseline in seizure frequency was assumed to be 0.195 for placebo and 0.492, 0.670, 0.754, and 0.780 for the 50mg bid, 100mg bid, 200mg bid, and 400mg bid doses of PSL, respectively. A common SD of 0.985 was assumed. These estimates are based on prior experience in epilepsy together with the EP0069 study results.

With power of 90%, a 2-sided Type-1 error of 5%, and all dose groups of the same size, 80 subjects are required per arm, giving a total of 400 subjects.

Assuming a screening failure rate of approximately 20%, it is anticipated to enroll around 500 subjects and randomize 400 subjects in this study.

The study is also powered to give over 80% power to observe a statistically significant result for the 75% response rate. For the 75% responder rate, assumptions were a 0.121 responder rate for placebo and corresponding responder rates of 0.233, 0.301, 0.332, and 0.342 for the 50mg bid, 100mg bid, 200mg bid, and 400mg bid doses of PSL, respectively.

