## 3 DATA ANALYSIS CONSIDERATIONS

### 3.1 General presentation of summaries and analyses

Statistical analysis and generation of tables, figures, subject data listings, and statistical output will be performed using SAS Version 9.3 or higher. All tables and listings will use Courier New font size 9.

Descriptive statistics will be displayed to provide an overview of the study results. For categorical variables, the number and percentage of subjects in each category will be presented. Unless otherwise noted, all percentages will be displayed to 1 decimal place. No percentage will be displayed for zero counts, and no decimal will be presented when the percentage is 100%. For continuous variables, descriptive statistics will include number of subjects with available measurements (n), mean, SD, median, minimum, and maximum.

Decimal places for descriptive statistics will always apply the following rules:

- “n” will be an integer
- Mean, SD, and median will use one additional decimal place compared to the original data
- Minimum and maximum will have the same number of decimal places as the original value.

Unless otherwise specified, statistical tests of efficacy variables will be presented as two-sided p values rounded to three decimal places. P-values less than 0.001 will be presented as “<0.001” and p-values greater than 0.999 will be presented as “>0.999.” Statistical comparisons will be two-sided and will be performed at the 0.05 level of significance.

A complete set of data listings containing all documented data as well as calculated data (e.g., change from Baseline), as applicable, will be generated.

Treatment groups will be displayed as: Placebo, PSL 50 mg bid, PSL 100mg bid, PSL 200mg bid, and PSL 400mg bid.

Log-transformation is based on natural logarithm. For analyses on log-transformed values, model estimates will be back-transformed to anti-log space for table presentation. See Section 8.1.1 for details.

Data collected at scheduled visits will be included the by-visit summary. Data collected at unscheduled visits will not be included in the by-visit summary, but will be considered when determining the Last Visit, minimum, and maximum post-Baseline values during the Treatment Period. Data collected on Visit 8 will be summarized separately for subjects in the Conversion Period versus the Taper and Safety FU Period.

In general, all CRF data will be presented in the subject listings.

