#### **8.1.2.4.3 Sensitivity analysis 3: multiple imputation**

After the multiple imputation process described in Section 8.1.2.2.2, seizure frequency during the Maintenance Period will be calculated as  $[\exp(\log\text{-transformed seizure frequency}) - 1]$  and the 75% responder status will be derived. Multiple imputed datasets will be analyzed using the same logistic regression model as in the primary analysis for the MAR imputation and control-based imputation respectively. If there are issues with model convergence, covariates will be dropped sequentially in the order of Region, and then Baseline SV2A use (Yes or No) if further needed. The tipping point analysis based on MAR multiple imputation will be repeated until

none of the PSL treatment group is significantly different from placebo based on the logistic regression model.

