### **8.3.2.1 Change from Baseline in log-transformed observable focal-onset seizure frequency over the first 4 weeks, second 4 weeks, and third 4 weeks of the 12-week Maintenance Period**

The 28-day adjusted seizure frequencies during the Treatment Period will be computed using observed diary records for the following 4-week intervals: Visit 2 to Visit 4, Visit 4 to Visit 5, Visit 5 to Visit 6, and Visit 6 to Visit 7. The 28-day adjusted seizure frequency during the Treatment Period and change from baseline based on the observed data will be summarized descriptively by the 4-week interval.

The change from Baseline in log-transformed observable focal-onset seizure frequency by 4-week interval will be analyzed using a Mixed Model Repeated Measures (MMRM) model, including Baseline log-transformed seizure frequency as a continuous fixed effect covariate, and treatment, Region (Europe or Non-Europe), Baseline SV2A use (Yes or No), and visit as fixed effect factors, and Baseline  $\times$  visit and treatment  $\times$  visit interactions. MMRM assumes that missing data are missing at random and estimates the mean outcome at each time interval by treatment group. An unstructured covariance structure will be used. If the model does not converge, an appropriate covariance structure will be used instead. Estimates of effects and comparison contrasts and CI will be back-transformed for display in tables as described in Section 8.1.2.1.

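### The FDA/PMDA primary effect, tabulated as percent reduction over placebo, is a reduction in (28-day seizure frequency + 1), so it understates the between-arm reduction in seizure frequency and needs a correct label and an offset-free companion

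*SAP*

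**What the plan says.** Protocol 13.3.1.1 sets the analysis scale as ln(x+1), "where x represents the 28-day seizure frequency". SAP 8.1.1.2 repeats this: "The 28-day adjusted seizure frequency value will be log-transformed using the function" ln(x+1), and the change from Baseline is ln(SFT+1) − ln(SFB+1).

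SAP 8.1.2.1 fits the ANCOVA on that scale. The effect to be tabulated, named as a percent reduction over placebo, is 100 × (1 − exp(diff)). The SAP defines the input to that formula in these words: "where diff is the model estimate of the log ratio between each PSL group and placebo group". The confidence limits are to be shown as exp(lower) and exp(upper).

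SAP 3.1 gives a general rule that "model estimates will be back-transformed to anti-log space for table presentation. See Section 8.1.1 for details", but the current Section 8.1.1 contains no back-transformation. SAP 8.3.2.1, the repeated-measures model by 4-week interval, adopts the same display: "Estimates of effects and comparison contrasts and CI will be back-transformed for display in tables as described in" Section 8.1.2.1.

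None of this text says that the ratio is of (frequency + 1), and none of it takes the 1 off the treatment contrast.

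**The concern.** A reader who sees percent reduction over placebo beside an endpoint called seizure frequency will take it as the reduction in seizure frequency. It is not quite that. The added 1 inflates both arms, and proportionally more in the arm with fewer seizures, so the ratio is pulled towards 1 and the reduction looks smaller than it is.

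This figure is the displayed effect size of the FDA/PMDA primary variable, which is also an EMA secondary variable. What is at stake is the accuracy of that reported effect, not the inference.

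The same sentence group also mixes scales. The point estimate is a percent reduction, while its limits are ratios, so the estimate and its interval cannot be read side by side.

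**Working it through.** **Inputs.** SAP 2.7 (same figures in Protocol 13.8): "The log-reduction from Baseline in seizure frequency was assumed to be 0.195 for placebo and" 0.492, 0.670, 0.754 and 0.780 for 50, 100, 200 and 400mg bid; common SD 0.985; 80 per arm; 90% power; two-sided 5%; Hochberg. The entry minimum is 4 observable focal-onset seizures per 28 days (Protocol 6.1, criterion 6). Every other Baseline level below is an assumption, because the documents give none.

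**Step 1: reproduce the plan's own figure.** For 200mg bid the difference is 0.754 − 0.195 = 0.559. At two-sided 0.025 and 90% power:

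n = 2 × [(2.2414 + 1.2816) × 0.985/0.559]² = 77.1, so 78 per arm against the stated 80.

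Simulating Hochberg over the three upper doses at 80 per arm gives power of about 0.91 for (400 and 200) or (200 and 100), against the stated 90%. The inputs are being read as the plan intends.

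**Step 2: what the rule reports.** For 400mg bid, diff = −(0.780 − 0.195) = −0.585. Then 100 × (1 − exp(−0.585)) = 100 × (1 − 0.557) = 44.3%.

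**Step 3: what exp(diff) is.** Let m0 and m1 be the back-transformed placebo and PSL frequencies, each exp(mean of ln(SF+1)) − 1. Then

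exp(diff) = (m1 + 1)/(m0 + 1), so 1 − exp(diff) = (m0 − m1)/(m0 + 1) = (1 − m1/m0) × m0/(m0 + 1).

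The tabulated figure is the frequency reduction times m0/(m0+1), which is below 1 for any finite m0. If diff were positive, an increase would be understated in the same way.

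**Step 4: size at a Baseline level B.** m0 = (B+1)exp(−0.195) − 1 and m1 = (B+1)exp(−r) − 1, with r the dose's log reduction. Worked case, B = 10 and 400mg bid: m0 = 8.05, m1 = 4.04, 1 − 4.04/8.05 = 49.8%. Check: 49.8% × 8.05/9.05 = 44.3%.

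| Dose | SAP rule | B = 10 | B = 20 | B = 40 | B = 4 (entry floor) |
|---|---|---|---|---|---|
| 50mg bid | 25.7% | 28.9% | 27.3% | 26.5% | 33.9% |
| 100mg bid | 37.8% | 42.5% | 40.1% | 39.0% | 50.0% |
| 200mg bid | 42.8% | 48.1% | 45.5% | 44.1% | 56.6% |
| 400mg bid | 44.3% | 49.8% | 47.0% | 45.6% | 58.5% |
| m0/(m0+1) | – | 0.89 | 0.94 | 0.97 | 0.76 |

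**Step 5: dose spacing.** The factor m0/(m0+1) does not depend on the dose. Relative to 400mg bid, the lower three doses stand at 0.58, 0.85 and 0.97 under the SAP rule, and at the same ratios in every other column.

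**Step 6: subject-level check.** Cut every subject's frequency by the same true 44.3%, with lognormal placebo frequencies (assumed medians 4 to 15, log SD 0.8 to 1.1). The SAP rule displays 33.9% to 40.8%. Rebuilding the reduction from exp(mean) − 1 in each arm gives 41.4% to 43.5%, which is closer but still slightly low.

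**The case against.** The strongest case on the other side is that 100 × (1 − exp(diff)) is a conventional display, that transform and formula are both stated exactly, and that the label does not literally add *in seizure frequency*. Offset-free results are also planned elsewhere: percent reduction per subject (SAP 8.1.1.3, 8.2.1.3), seizure frequency by period (8.3.2.23) and responder rates. Any replacement has its own faults. It needs a reference Baseline, it is itself approximate (Step 6), and its interval need not agree with the ANCOVA p-value at the boundary. All of that stands. It means the conventional figure should not be thrown out. It does not make an unqualified label accurate.

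Four stronger readings are tempting, and the documents do not support them.

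- *The rule flattens the dose response.* Gaps in percentage points narrow, but Step 5 shows that order and relative spacing are unchanged.
- *The offset is what makes the figure non-comparable with the percent-reduction secondary.* That secondary is a Hodges-Lehmann median difference in within-subject percent reductions. It is a different quantity from a between-arm ratio with or without the offset.
- *The SAP contradicts itself because in 8.1.2.4.3 "seizure frequency during the Maintenance Period will be calculated as" exp(·) − 1.* That step inverts each subject's imputed value in order to derive responder status. It is not a rule for a treatment contrast.
- *The shortfall is about 14 points.* That needs a typical Baseline of 4, which every subject must at least reach. Assumed lognormals (medians 4 to 10, log SD 0.8 to 1.1) truncated at 4 give a typical level of about 8 to 15, and a gap of about 7 down to 3.6 points for 400mg bid.

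**Conclusion.** The point holds as one of labelling and estimation. As written, SAP 8.1.2.1 reports the percent reduction in (28-day frequency + 1), which is smaller in size than the between-arm reduction in seizure frequency by the factor m0/(m0+1). No current text corrects or flags this.

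Under the plan's own 400mg bid assumption, the understatement is 5.5 points at Baseline 10, 2.7 at 20 and a little over 1 at 40. These sizes rest on assumed Baseline levels and on the planning log reductions. The actual size depends on the placebo-arm frequency and cannot be known from the documents.

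A reader might infer that the primary result itself is at risk. It is not. Tests, p-values, Hochberg decisions and sample size all stay on the ln(x+1) scale, and the understatement runs towards no effect, so it cannot manufacture an efficacy claim. The change is still worth making, because it corrects the headline effect size at very little cost.

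**What to change.** In SAP 8.1.2.1, and in 8.3.2.1 which reuses the rule:

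- Keep 100 × (1 − exp(diff)), but label it *percent reduction over placebo in (28-day seizure frequency + 1)*.
- Give its limits on the same scale, 100 × (1 − exp(upper)) to 100 × (1 − exp(lower)), in place of exp(lower) and exp(upper).
- Beside it, report for each arm exp(LS mean of ln(SF+1) at the mean Baseline covariate) − 1, and the percent reduction 100 × [1 − SF_PSL/SF_placebo] derived from those values, with a delta-method or bootstrap interval. State the Baseline level it refers to and that it is approximate.
- Leave the ANCOVA test and the multiplicity procedure as they are.

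The cost is a few lines of SAP text and programming. The small downside is one extra descriptive estimate whose interval may not match the ANCOVA p-value exactly at the boundary.
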